In this hypothetical strategy, the event of withdrawing CT-152+ADT or sham+ADT is considered missing at random (MAR), and the primary endpoint of the trial could be considered as a combination of the measurements of on-treatment completers at Week 6 and the imputation of the endpoint to Week 6 following the trend in each treatment group using the mixed model repeated measurements (MMRM) method to impute missing data for subjects who withdraw CT-152+ADT or sham+ADT during the trial. All data collected during the trial treatment period will be used for statistical analysis. For the primary efficacy analysis, the treatment effect will be estimated using the MMRM method described in Section 9.4.1.1.2. Under the MAR assumption, MMRM provides an unbiased estimate of treatment effect for the treatment period. Analyses with missing values imputed by multiple imputation under missing not at random (MNAR), and other methods will be performed as sensitivity analyses.

Protocol No. 345-201-00002

9.4.1.1.2 **Primary Analysis Method**

The primary analysis will utilize a MMRM with treatment, visit, treatment by visit interaction, and site as fixed effects to assess heterogeneity of treatment effects. This model will also include an interaction term of visit by baseline MADRS total score as a covariate. Observed data from all planned visits during the 6-week treatment period will be included in the model. An unstructured covariance matrix will be used to model the within subject variance. The primary comparison between the CT-152+ADT or sham+ADT at Week 6 will be estimated as the difference between least squares means utilizing the computing software SAS procedure PROC MIXED.

The mathematical formula for the MMRM model is as follows:

$$y = X\beta + Zu + \epsilon$$

Where

y denotes the observed vector of change from baseline to Week 6 in MADRS total score;

X is the known matrix for the fixed effects and covariate;

 β is an unknown fixed-effect parameter vector;

Z is the known matrix for the random effect of subject;

u is an unknown vector of random effect of subject with mean 0 and variance-covariance matrix **G** (unstructured covariance matrix);

 ϵ is an unknown vector of random errors with mean 0 and variance **R**.

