9.4.1.2.2 Efficacy Endpoints for Assessment of Durability

The durability of effect of CT-152 will be assessed based on MADRS total score and GAD-7 total score.

Protocol No. 345-201-00002

It will include 3 MADRS assessments at Weeks 6, 8, and 10. In addition to demonstrating an MCID group difference of 1.6 to 1.9 at Week 6 with statistical significance, durability will be demonstrated by a point estimate of the difference in change from baseline at Weeks 8 and 10 above 1.6, when comparing CT-152 and sham. Such point estimates will be provided using the same MMRM model in the primary efficacy analysis with change from baseline in MADRS total score at Week 8 and 10 as the dependent variable.

Durability based on GAD-7 will also include 3 assessments, at Weeks 6, 8, and 10, demonstrating a numerically larger improvement on point estimate of the difference in change from baseline in GAD-7 total score at Weeks 8 and 10 in CT-152 compared to sham. Such point estimates will be provided using the same MMRM model in the key secondary efficacy analysis with change from baseline in GAD total score at Week 8 and 10 as the dependent variable.

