# 8.2.1 Efficacy Endpoints for Assessment for Durability

The durability of effect of CT-152 will be assessed based on MADRS total score and GAD-7 total score.

It will include 3 MADRS assessments at Weeks 6, 8, and 10. In addition to demonstrating an with statistical significance, durability will be demonstrated by a point estimate of the difference in change from baseline at Weeks 8 and 10 when comparing CT-152 and sham. Such point estimates will be provided using the same MMRM model in the primary efficacy analysis with change from baseline in MADRS total score at Week 8 and 10 in the extension period as the dependent variable.

Durability based on GAD-7 will also include 3 assessments, at Weeks 6, 8, and 10, demonstrating a numerically larger improvement on point estimate of the difference in change from baseline in GAD-7 total score at Weeks 8 and 10 in CT-152 compared to sham. Such point estimates will be provided using the same MMRM model in the key secondary efficacy analysis with change from baseline in GAD total score at Week 8 and 10 in the extension period as the dependent variable.

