## 2 Removing Key Secondary Efficacy Endpoint

The change from baseline to Week 6 in GAD-7 total score, mentioned in Section 8.2 in the original SAP, will be considered as a secondary efficacy endpoint rather than the key secondary efficacy endpoint in this study. The hierarchical testing approach used to control the overall type-I error rate on the primary efficacy endpoint and the key secondary efficacy endpoint will no longer be applicable.

To control the overall type I error for the primary efficacy endpoint, it will be tested at a significance level of 0.049 (2-sided) as planned. All rest efficacy endpoints, including secondary efficacy, other efficacy, and CCI , will be tested at a nominal 0.05 level (2-sided) individually without adjusting for multiplicity.

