Durability based on GAD-7 will also include 3 assessments, at Weeks 6, 8, and 10, demonstrating a numerically larger improvement on point estimate of the difference in

Confidential - Proprietary Information

7

change from baseline in GAD-7 total score at Weeks 8 and 10 in CT-152 compared to sham. Such point estimates will be provided using the same MMRM model in the key secondary efficacy analysis with change from baseline in GAD-7 total score at Week 8 and 10 as the dependent variable.

One unblinded IA for assessment of efficacy will be conducted on approximately the first 180 (50%) randomized subjects. This unblinded IA will be carried out when these subjects have either completed the Week 6 visit or discontinued prior to Week 6. The O'Brien-Fleming boundaries³ will be utilized in primary analysis for the rejection of the null hypothesis to maintain an overall nominal significance level of 0.05 (2-sided). The boundary values for the rejection of the null hypothesis are given in Table 2.2-1. Also, to control the overall type I error, the statistical tests based on the primary efficacy endpoint and the key secondary efficacy endpoint will be done using a hierarchical approach. The primary hypothesis will be tested at the 0.003 level at IA and if successful in rejecting the null hypothesis, analysis of the key secondary endpoint will be tested at the type I error level of 0.003. Similar rules will be carried out at the final analysis with the 0.049 level if the trial doesn't stop at IA. Should the primary outcome not achieve statistical significance, the key secondary endpoint will be categorized as other efficacy endpoint.

Table 2.2-1 Boundaries for Rejection of the Null Hypothesis for the Interim and Final Analyses

Analysis	Two-sided Alpha Level 
Interim analysis #1 (~ 50%)	0.003
Final analysis (100%)	0.049

<sup>1 Obtained using PASS 14(2015) sample size software.

The fraction of the sample size might not be consistent with the fraction of the information when the primary analysis is MMRM with high dropout rate. If there is a high dropout rate, the timing for the IA will use the rate of those subjects who complete the Week 6 assessment which would control the Type I error with the alpha spending function.

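### The GAD-7 durability criterion asks only for favourable point estimates at Weeks 8 and 10, with no Week 6 criterion, so a statement resting on it would carry little evidence that an anxiety effect exists or has lasted.

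*SAP*

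**What the plan says.** **GAD-7.** SAP 8.2.1 describes durability on this scale as "demonstrating a numerically larger improvement on point estimate of the difference in change from baseline in GAD-7 total score". The comparison is CT-152 against sham, and it applies to both extension visits, Weeks 8 and 10. Protocol 9.4.1.2.2 and section 2.2 of the Interim Analysis Plan (IAP) give the same criterion, and the protocol synopsis and Table 3-1 repeat it. Week 6 is named ("Durability based on GAD-7 will also include 3 assessments, at Weeks 6, 8, and 10"), but nothing has to be shown there. No margin, test or interval enters the criterion.

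**MADRS.** The preceding paragraph of Protocol 9.4.1.2.2 is stricter. It begins "In addition to demonstrating an MCID group difference of 1.6 to 1.9 at Week 6 with statistical significance" and continues "durability will be demonstrated by a point estimate of the difference in change from baseline at Weeks 8 and 10 above 1.6". IAP 2.2 repeats the 1.6 margin. The matching SAP sentence has gaps that look like redaction, and nothing here relies on them.

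**Addendum.** Section 2 of the SAP Addendum says the Week 6 GAD-7 change "will be considered as a secondary efficacy endpoint rather than the key secondary efficacy endpoint". It ends the hierarchy and tests every efficacy endpoint other than the primary at a nominal two-sided 0.05. Section 4 adds supportive durability endpoints for MADRS only. The GAD-7 durability wording is left as it was.

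**The concern.** Durability presupposes an effect that can last. The GAD-7 criterion does not ask whether there was one at Week 6, and any difference above zero at the two later visits satisfies it. Those visits are two weeks apart in the same subjects, so their estimates probably move together, and two favourable signs are then worth little more than one.

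The criterion can therefore be met when there was never an anxiety effect, or when there was one and it has gone. A reader who sees GAD-7 durability beside MADRS durability could take the two statements to rest on similar evidence, which they would not.

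**Working it through.** **The plan's own figure.** The documents give no operating characteristic for the GAD-7 criterion. The stated MADRS sample size (SAP section 4: difference 3, SD 9, 85% power, two-sided 0.05) reproduces:

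- n per arm = 2 × (1.960 + 1.036)² × 9² / 3² = 161.6, so 162 per arm and 324 in total; 324 / 0.9 = 360 randomized.
- SE of the difference = 9 × √(2/162) = 1.0. The planned effect is thus a drift (true difference divided by SE) of 3, with power Φ(3 − 1.96) = 85%.

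**Inputs for GAD-7.** No GAD-7 SD, effect size or between-visit correlation is given. The model covariance is open ("An unstructured covariance matrix will be used to model the within subject variance"). I therefore assume a correlation ρ between the treatment-difference estimates and show a range. Where Week 6 enters, the three visits are assumed equally correlated.

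**1. No GAD-7 effect at any visit.** The Week 8 and Week 10 estimates are bivariate normal with mean zero, so

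P(both favour CT-152) = 1/4 + arcsin(ρ) / (2π).

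At ρ = 0.6 this is 0.25 + 0.6435/6.2832 = 0.352. At the limits it is 25% (ρ = 0) and 50% (ρ = 1). Neither N nor SD appears, so enlarging the trial to 540 would not lower it. Simulation at 162 per arm gave 35.0% (ρ = 0.6) and 42.6% (ρ = 0.9).

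**2. A favourable Week 6 estimate read into the criterion.** P(all three favour CT-152) = 1/8 + 3 arcsin(ρ) / (4π). At ρ = 0.6 this is 0.125 + 0.154 = 0.279.

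**3. Week 6 significant (two-sided 0.05, in favour of CT-152) and both later estimates favourable.** Trivariate normal probability under no effect.

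**4. Vanished effect.** Week 6 drift 3, drift 0 at Weeks 8 and 10; proportion meeting the criterion among trials with a significant Week 6 result (simulation).

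| ρ | 1. As written, no effect | 2. Favourable Week 6 implied, no effect | 3. Significant Week 6 required, no effect | 4. As written, effect vanished |
|---|---|---|---|---|
| 0.6 | 35.2% | 27.9% | 2.3% | 41% |
| 0.7 | 37.3% | 31.0% | 2.4% | 44% |
| 0.8 | 39.8% | 34.6% | 2.5% | 47% |
| 0.9 | 42.8% | 39.2% | 2.5% | 50% |

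**5. MADRS rule in situation 4.** With SE 1.0, a significant Week 6 estimate exceeds 1.96 and so already clears the 1.6 to 1.9 range. Both later estimates must then exceed 1.6 by chance, which happens in about 2-3% of such trials for ρ 0.6-0.8.

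**6. What stricter GAD-7 rules would cost.** Suppose the effect is real and persists at drift 3 at all three visits.

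- As written: each later estimate is favourable with probability Φ(3) = 0.9987, so both are in at least 1 − 2 × 0.0013 = 99.7% of trials.
- Significant Week 6 added: about 85%, which is the Week 6 power.
- 95% CIs excluding zero at Weeks 8 and 10 also required: 71-79% (ρ 0.6-0.9).
- MADRS rule at the same drift: 78-83%.

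**The case against.** The best defence is that no formal decision uses this criterion. Trial success rests on the MADRS primary endpoint, the efficacy stop uses the MADRS p-value and MADRS estimates, and conditional power is computed on MADRS alone. Under the Addendum every other efficacy endpoint is nominal. That stands. A reader might infer that 35-43% is a false-positive rate for the trial; the documents do not support this.

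A reader might also infer that the Addendum loosened GAD-7 durability by ending "The hierarchical testing approach used to control the overall type-I error rate on the primary efficacy endpoint" and the key secondary endpoint. It did not: the hierarchy governed the Week 6 GAD-7 test, and no section placed the Week 8 and Week 10 comparison behind it.

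The wording can be read more mildly too. Grammatically, 'demonstrating' governs a numerical improvement rather than durability, and 'numerically' suggests description. But the sentence opens with durability on GAD-7 and follows the MADRS rule with 'also', so reading it as a criterion is natural. The ambiguity is itself a reason to reword.

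Week 6 is listed and separately tested, so a reader would see that result. Even if a favourable Week 6 estimate is implied, the no-effect rate is 28-39%. The illustrative SAS code in SAP 8.1.2 requests confidence limits, so intervals may well be produced, but the criterion does not use them.

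Finally, it is tempting to demand intervals excluding zero at Weeks 8 and 10. The MADRS rule does not ask that of the primary scale, and at SE 1.0 its 1.6 margin is less demanding than 1.96 SE. Consistency with MADRS does not justify the demand.

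**Conclusion.** The concern holds as one about the strength of a GAD-7 durability statement, and no further. As written, the criterion is met in 25-50% of trials with no GAD-7 effect for any non-negative ρ. The narrower 35-43% depends on an assumed ρ of 0.6-0.9 that no document supplies. After a significant Week 6 effect that has since vanished, it is met in about 41-50%, assuming drift 3 at Week 6 and equal correlations of 0.6-0.9. Over the whole non-negative range the criterion remains weak evidence of any effect, so the conclusion does not turn on the choice of ρ.

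**What to change.** Make the same change in Protocol 9.4.1.2.2, SAP 8.2.1 and IAP 2.2, and in the repeats in the synopsis and Table 3-1:

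- State GAD-7 durability only if the Week 6 GAD-7 difference is significant in favour of CT-152 at the nominal two-sided 0.05 level that the Addendum sets. The MADRS rule already requires Week 6 significance. This lowers the no-effect rate to about 2.4%.
- This condition cannot detect an effect that has vanished: the 41-50% already presumes a significant Week 6 result. So report the Week 8 and Week 10 differences with 95% CIs as descriptive, and replace 'demonstrating' with wording such as 'described by'.
- Do not require those CIs to exclude zero, which would hold the secondary scale to a stricter durability standard than the primary.

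The cost is document wording; no data, visits or sample size change. The downside is that a GAD-7 durability statement becomes somewhat harder to make: for a persistent effect of drift 3 it would be available in about 85% of trials, against nearly all as written. With a smaller Week 6 effect it would be available less often, and the documents give no GAD-7 assumptions from which to say how much less.

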# 8.3 Other Efficacy Endpoints

Other efficacy analyses are listed below. All other efficacy endpoints will be evaluated at a nominal 0.05 level (2-sided) without adjusting for multiplicity.

- 1) Change from baseline to Weeks 2 and 4 in the MADRS total score
- 2) Change from baseline to Weeks 2 and 4 in the GAD-7 total score
- 3) Change from baseline to Weeks 2, 4, and 6 in the CGI-S score.
- 4) Change from screening to Weeks 4 and 6 in the PHQ-9 total score.

- 5) Change from baseline to Week 6 in the WHODAS 2.0 total score.
- 6) MADRS response at Weeks 2, 4, and 6, where response is defined as ≥ 50% reduction in MADRS total score from baseline
- 7) MADRS partial response at Weeks 2, 4, and 6, where partial response is defined as ≥ 30% and < 50% reduction in MADRS total score from baseline
- 8) MADRS response at Weeks 8 and 10 , where response is defined as full or partial, and defined as  $\geq$  30% reduction in MADRS total score from baseline.

Endpoints (1) through (4) will be evaluated using the same MMRM model described in the primary analysis. The LOCF and OC analyses using ANCOVA will also be conducted. The LOCF analysis model includes treatment and trial site as main effects, and baseline value as covariate. For the OC analyses, trial site will not be included in the model.

Endpoint (5) will be evaluated using ANCOVA with baseline as covariate and treatment and, in LOCF analyses, trial site as main effects. Endpoints (6) through (7) will be evaluated by Cochran-Mantel-Haenszel (CMH) General Association Test controlling, in LOCF analyses, for trial site. OC analyses will also be conducted for variables (5) through (7) but will not control for trial center.

Endpoint (8) will be analyzed using descriptive statistics on LOCF dataset.

# 8.6 Interim Analysis and Adaptive Design

An unblinded interim analysis of efficacy data will be conducted on approximately the first 180 randomized subjects. The unblinded interim analysis will be carried out when these subjects have either completed the Week 6 visit or discontinued prior to Week 6. The difference between CT-152 and sham based on the primary efficacy endpoint will be tested at the unblinded interim analysis. The sponsor will remain blinded to the IA results, and will only receive DMC's recommendation as per the interim analysis plan (IAP) and the DMC charter.

To protect the overall type I error at the 2-sided alpha level of 0.05 (2-sided) and to limit the estimation bias, the O'Brien-Fleming spending function will be used for this two-stage group sequential design. A significance level of 0.003 (2-sided) will be allocated to this unblinded interim analysis. The corresponding final significance level is 0.049 (2-sided).

Based on the primary analysis result at IA, the DMC will be allowed to make recommendations based on 1 of the 4 outcomes:

- Early stop for efficacy if the unblinded interim analysis p-value is < 0.003 (2-sided; Early Efficacy), and all point estimates of difference in change from baseline to Weeks 6, 8, and 10 in MADRS total score are above 1.6.
- Proceed as planned to 360 randomized subjects if the conditional power observed at the unblinded interim analysis is ≥ 85%; or is > 15% and ≤ 50% (Favorable or Unfavorable Zone).
- Increase sample size from 360 randomized subjects to 540 randomized subjects, if the conditional power observed at the unblinded interim analysis is > 50% but < 85% (Promising Zone).
- Early stop for futility if the conditional power observed at the unblinded interim analysis is ≤ 15% (Futility).

The sample size will be re-estimated only based on the conditional power determined at the interim analysis. The adaptive designs methodology published by Chen, DeMets, and Lan

(2004) will be used to increase the sample size based on an interim estimate of the treatment effect size, possibly combined with other external information, without inflating the type I error.

If the study is terminated after claiming efficacy in the interim analysis, a "final" analysis will be performed. This "final" analysis will include the efficacy data occurring between the data cutoff for the interim analysis and the final database lock (i.e. all efficacy data up to database lock), and the alpha level for the "final" analysis will be derived based on the information fraction using the Lan-DeMets Spending Function with O'Brien-Fleming boundary.

In this SAP, the statistical tests based on the primary efficacy endpoint and the key secondary efficacy endpoint will be done using a hierarchical approach, in order to control the overall type I error rate. In this hierarchical testing, the alpha-spending for the primary endpoint will be applied to the key secondary endpoint. Specifically, if the trial stops at the IA, the key secondary endpoint will be tested on the IA data at a two-sided 0.003 level.

If the trial does not stop at the IA, the above sequence of testing will be repeated for the final analysis with the use of a two-sided 0.049 significance level. That is, at the final analysis, the primary efficacy endpoint will be tested at a two-sided 0.049 significance level, and upon achieving significance on the primary endpoint, the key secondary endpoint will be tested at the same level. In that scenario, the final analysis will be conducted using the data of approximately 360 or 540 (if sample size is adapted) subjects. There will be no data accrual after the database lock for the final analysis.

# 9 Safety Analysis

Standard safety variables to be analyzed include AEs and clinical laboratory tests. In addition, suicidality will be evaluated through analysis of data from appropriate scales.

Analyses of the treatment period and extension period safety data will be performed on the Safety Sample unless indicated otherwise. In general, baseline of a safety variable is defined as the last observation of the variable prior to the start of double-blind digital therapeutic, unless specified otherwise.

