7.3.2 Treatment Discontinuation

After CT-152 or sham assignment, a subject may stop CT-152 or sham permanently for a variety of reasons. Treatment discontinuations may be initiated by a subject who is not satisfied with treatment or may become medically necessary due to AEs, require treatment with a prohibited medication or therapy, or other issues, as determined by the investigator.

When a subject discontinues or is withdrawn from the trial, the investigator will perform a final assessment, including the procedures indicated in the schedule of assessments (Table 1.3-1) for Day 42 as well as subject debriefing (subjects who discontinue early before Week 6) or Day 70 (subjects who discontinue early from the trial after Week 6). The Day 42 or Day 70 procedures should be performed on the last day the subject utilizes the double-blind digital mobile application or as soon as possible after the subject discontinues in order to complete all safety and effectiveness measurements.

In the event that a subject discontinues, every effort will be made by the investigator to determine why a subject fails to return for necessary visits or is dropped from the trial to record the reasons for withdrawal as thoroughly as possible. Reasonable efforts will be made by trial site staff to retain subjects in the trial and to complete remote visits and telephone contacts. Efforts will include outreach via telephone or e-mail when a subject misses a remote visit or telephone contact and rescheduling missed remote visits and telephone contacts within the \pm 3 day visit window.

The digital mobile application on the discontinued subject's smartphone device will be uninstalled as described in Section 6.2.1.

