# 5 Data Sets for Analysis and Missing Data

## 5.1 Data Sets for Analysis

The following analysis datasets are defined for this trial:

Enrolled Sample – all subjects enrolled in the trial.

- Randomized Sample all subjects allocated based on the randomization process and recorded in the database. Subjects treated without being randomized will not be considered as randomized and therefore will not be included in any efficacy or safety population analyses.
- Safety Sample all randomized subjects who receive at least 1 occurrence of either CT-152 or sham use. All safety assessments will be performed on the safety analysis set. If any subjects receive a treatment that differs from the assigned treatment, then the safety analyses will be conducted on the treatment actually received.
- FAS Sample all randomized subjects who receive at least 1 occurrence of either CT-152 or sham use, and have baseline and at least 1 postbaseline assessment of MADRS total score. Subjects included in FAS Sample are defined as evaluable subjects.
- Per-protocol (PP) Analysis Sample all subjects in the FAS Sample who were treated for 6 weeks, did not have a major protocol deviation, and were adherent to CT-152 or sham treatment in this trial. The classification of protocol deviations will be established in a blinded review by the sponsor in a meeting prior to breaking the blind. Specifically, the following criteria will be used to exclude subject from PP analysis sample.
  - 1. Subjects in the FAS Sample but not treated for 6 weeks

- 3. Subjects who reported concomitant medication use that will impact the primary efficacy and key secondary endpoints
- 4. Subjects who had major protocol deviation that will impact primary efficacy and key secondary endpoint
- 5. Subject who received the wrong study digital therapeutic

The PP Analysis Sample will only be used for sensitivity analysis of the primary efficacy and key secondary variables.

The core dataset for all efficacy analyses is the FAS Sample, which is created based on the intent-to-treat (ITT) principle. However, as will be described below, in order to handle missing data and restrictions imposed by different types of analyses (e.g., change from baseline analysis), other datasets derived from the FAS dataset will be used for the efficacy analyses.

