#### 9.1 Adverse Events

All adverse events (AEs) will be coded by system organ class (SOC) and Medical Dictionary for Regulatory Activities (MedDRA) Preferred Term (PT). The incidence of the following events in the treatment period and the extension period will be summarized by treatment group and overall:

a) Treatment-emergent AEs (TEAEs)

- b) TEAEs by severity
- c) TEAEs potentially causally related to the digital therapeutic (CT-152 or sham)
- d) TEAEs with an outcome of death
- e) Serious TEAEs
- f) TEAEs leading to discontinuation of the digital therapeutic (CT-152 or sham)

Deaths, SAEs, and AEs leading to discontinuation from digital therapeutic or trial, will be listed by subject on the Safety Sample.

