#### 9.1.2 Adverse Events in the Extension Period

TEAEs in the extension period are defined as AEs with an onset date during that period, or if the event was continuous from the treatment period and was worsening, serious, study digital therapeutic related, or resulted in death or discontinuation. AEs occurring through the last subject visit or contact in this period will be included in these summary tables.

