# 9.3 Suicidality Data

Suicidality will be monitored during the study using the C-SSRS and will be summarized as number and percentage of subjects reporting any suicidal behavior, ideation, behavior by type (4 types), ideation by type (5 types) and treatment emergent suicidal behavior and ideation. Summary will be provided for the treatment period and extension period on the Safety Sample.

Suicidality is defined as report of at least one occurrence of any type of suicidal ideation or at least one occurrence of any type of suicidal behavior during assessment period (count each person only once).

Treatment emergent suicidal behavior and ideation is summarized by four types: Emergence of suicidal ideation, Emergence of suicidal ideation, Worsening of suicidal ideation, Emergence of suicidal behavior.

Emergence of suicidal behavior/ideation is defined as report of any type of suicidal behavior/ideation during treatment when there was no baseline suicidal behavior/ideation.

Emergence of serious suicidal ideation is defined as observation of suicidal ideation severity rating of 4 or 5 during treatment when there was no baseline suicidal ideation.

Worsening of suicidal ideation is defined as a suicidal ideation severity rating that is more severe than it was at baseline.

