## 9.3.1 Clinically important suicidality

Clinically important suicidality may include:

- 1) Suicidal behavior (with or without intent of suicide or serious self-harm)
- 2) Acute suicidality to such a degree that precaution against suicide must be exercised.
- Response of "yes" to C-SSRS ideation items 4 or 5 or any of the C-SSRS behavioral items.
- 4) Score of "4", "5", or "6" on the MADRS suicidal thoughts item.
- 1) and 2) are referred to suicidality-related AEs, which will be identified using Standardized MedDRA Query (SMQ) for suicidality.

The incidence of emergent clinically important suicidality will be compared between CT-152 and sham groups using Cochran-Mantel-Haenszel (CMH) General Association Test on OC dataset. Rates and 95% confidence intervals will be reported and the estimated differences between groups will be provided.

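### Descriptive extension-period AE and C-SSRS percentages are set on the whole Safety Sample, so subjects who left before the extension count as event-free

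*SAP*

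**What the plan says.** SAP section 9 sets the default analysis set for safety: "Analyses of the treatment period and extension period safety data will be performed on the Safety Sample unless indicated otherwise". SAP 5.1 defines that set as "all randomized subjects who receive at least 1 occurrence of either CT-152 or sham use", with no condition on reaching Week 6.

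For adverse events, SAP 9.1 plans: "The incidence of the following events in the treatment period and the extension period will be summarized by treatment group and overall". SAP 9.1.2 defines the events: "TEAEs in the extension period are defined as AEs with an onset date during that period", plus events continuing from the treatment period that worsen or meet certain other conditions. It sets the cut-off: "AEs occurring through the last subject visit or contact in this period will be included in these summary tables". It names no analysis set, so the section 9 default applies.

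For the C-SSRS, SAP 9.3 names the set itself: "Summary will be provided for the treatment period and extension period on the Safety Sample".

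SAP 9.3.1 is different. Emergent clinically important suicidality is to be "compared between CT-152 and sham groups using Cochran-Mantel-Haenszel (CMH) General Association Test on OC dataset".

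On subjects who leave, Protocol 7.3.2 says: "When a subject discontinues or is withdrawn from the trial, the investigator will perform a final assessment". Before Week 6, this consists of the Day 42 procedures and the debriefing. The notes to the Schedule of Assessments (Protocol Table 1.3-1) end AE collection at the last visit or contact and SAE collection 28 days after last use. The SAP addendum keeps the original conventions unless it states otherwise, and it does not touch safety denominators.

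**The concern.** A subject who leaves the trial before the extension cannot contribute a Week 8 or 10 C-SSRS or a nonserious AE with onset in Weeks 7 to 10. On the Safety Sample, that subject still sits in the denominator and reads as a subject without the event.

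The extension is the only scheduled observation after the EFMT and SMT exercises are withdrawn, so its tables are where a reader would look for events after the exercises stop. Dropout may also be related to the outcome. Under the protocol, a subject may leave because depression worsens (6.5.3), because clinically important suicidality emerges (8.2.2), or because augmentation is required (6.1.2). Such subjects would count as non-events in the extension suicidality percentages.

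The other planned outputs do not supply the missing denominator. Exposure is summarized for the treatment period only (SAP 9.6), completers are defined at Day 70 (Protocol 4.5), and no table of subjects entering the extension and no person-time rate is specified.

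**Working it through.** **The plan's figures.** No document gives an extension denominator, a rate of leaving before Week 6, or an expected AE or suicidality rate. The nearest figure is the 10% allowance in SAP section 4: 324 / (1 − 0.10) = 360 randomized, or 180 per arm. It reproduces, but it covers subjects without an evaluable MADRS, so it is not a rate of leaving before the extension. I use 180 per arm only as an illustrative Safety Sample size, and all dropout and event rates below are assumptions.

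**Formula.** Let r be the event rate among subjects who enter the extension and d the share of an arm's Safety Sample that leaves before it. If early leavers contribute no counted event:

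- reported rate = r × (1 − d)
- with equal r, reported ratio of arm B to arm A = (1 − d_B) / (1 − d_A)

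**Equal dropout, r = 10%.** Only the level changes, and the ratio stays at 1.00.

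- d = 5%: 0.95 × 10% = 9.5% in both arms
- d = 10%: 0.90 × 10% = 9.0% in both arms
- d = 20%: 0.80 × 10% = 8.0% in both arms

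**Unequal dropout, r = 10% in both arms.**

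| d, arm A | d, arm B | Reported A | Reported B | Ratio B/A |
|---|---|---|---|---|
| 10% | 20% | 9.0% | 8.0% | 0.89 |
| 5% | 20% | 9.5% | 8.0% | 0.84 |
| 10% | 30% | 9.0% | 7.0% | 0.78 |

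The arm with more dropout looks safer by 1.0 to 2.0 percentage points. With r = 5% the gaps halve, to 0.5 to 1.0 points. The percentages do not depend on arm size, so they are the same at 270 per arm.

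**A real excess can also be hidden.** With r = 12% and 75% entry in one arm, and r = 10% and 90% entry in the other, 0.75 × 12% = 9.0% and 0.90 × 10% = 9.0%. These values were chosen to cancel exactly; they show what is possible, not what is likely.

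**Effect of the change.** Nine events in an arm of 180 are reported as 9/180 = 5.0%. Among entrants:

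- d = 5%: 9/171 = 5.3%
- d = 10%: 9/162 = 5.6%
- d = 20%: 9/144 = 6.3%
- d = 30%: 9/126 = 7.1%

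**The case against.** **The denominator is inferred.** The SAP names an analysis set, not a percentage denominator, and SAP 9.1.2 names neither. This is true. For the AE tables the point rests on the section 9 default; for the C-SSRS summary the set is stated. With no extension-entrant set defined anywhere, the whole Safety Sample is the plain reading.

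**The suicidality comparison.** A reader might infer that this is diluted too. The documents do not support that. The CMH comparison in SAP 9.3.1, with its confidence intervals and group differences, uses the observed-cases dataset, which holds only recorded observations, and its period is not stated. It is outside this point. No between-arm test of extension AE rates is planned.

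**Early leavers at no risk at all.** This is also too strong. SAEs are collected to 28 days after last use, and Protocol 8.3.4.2 monitors immediately reportable events for 28 days after the last visit or contact. A subject whose last use was on Day 30, for example, is covered for SAEs to Day 58 (30 + 28), although SAP 9.1.2 leaves unclear whether such an event enters the extension table. For SAEs the dilution is therefore somewhat smaller than d. Stopping the app is also not leaving the trial: under Protocol 7.3.1 nonadherent subjects may remain with all procedures performed. Deaths and SAEs are listed by subject whatever the denominator.

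**Purpose of the extension.** Protocol 4.2 gives it as durability of effect, and psychotherapy content stays available in the CT-152 arm. The extension is not a designed study of treatment withdrawal, which limits how much weight these tables carry. It does not make the percentages right.

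**Selection.** Entry is a post-randomization event, so entrants may be a healthier subset and the arms are no longer the randomized groups. This stands, and it is why both numbers should be shown and the rates labelled descriptive.

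**Conclusion.** The point holds for the descriptive extension-period TEAE incidence tables and C-SSRS summaries. Following the plan as written understates both arms' extension rates by about the share of the arm that left before the extension, slightly less for SAEs.

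A reader might go further and infer a biased comparison of the arms. The documents do not establish one: that requires unequal dropout before the extension, and they give neither its size nor its direction. Under the assumed rates shown, the distortion is 0.5 to 2.0 percentage points. If few subjects leave, the effect is trivial. This is worth correcting because it is cheap, but it does not touch the primary analysis.

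**What to change.** In SAP 9.1.2 and 9.3, base extension-period percentages on Safety Sample subjects who entered the extension, meaning subjects who remained in the trial with at least one scheduled extension visit or telephone contact in Weeks 7 to 10. For the C-SSRS, require at least one extension-period C-SSRS. Tying entry to a scheduled contact keeps a late safety follow-up call from counting as entry and does not depend on the Week 6 visit having taken place.

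Show that number by arm beside the Safety Sample number in each extension table, and label the rates descriptive because entry is post-randomization. Keep all deaths and SAEs, including those after early withdrawal, in the Safety Sample listings. Leave the treatment-period tables unchanged.

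The cost is a short wording change and a population flag derived from data already collected. Extension percentages become slightly higher, and they describe a selected group.
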